4.3 Eligibility test procedure

Radiographs will be used to assess participants for Osteoarthritis using the Kellgren and Lawrence criteria which divide Osteoarthritis from mild to severe. It should be remembered that at the beginning of the disease, the radiographic appearance of the joint still looks normal. According to Kellgren and Lawrence, radiologically, osteoarthritis is classified as follows:

- 1) Grade 0: Normal, no signs of osteoarthritis
- 2) Grade 1: Doubtful, without osteophytes, doubtful joint narrowing

3) Grade 2: Minimal, few osteophytes on the tibia and patella and the joint surface is asymmetrically narrowed.

4) Grade 3: Moderate, there are moderate osteophytes in several places, the joint surface is narrowed, and subchondral sclerosis appears.

5) Grade 4: Severe, presence of large osteophytes, complete narrowing of the joint surface, severe subchondral sclerosis, and joint surface damage.

Mini Mental State Examination (MMSE) test will be used to assess the patient's cognitive abilities. This is important to ensure that patients can understand the instructions in the treatment process and the outcome measurement process.

5 Randomization, allocation and blinding

A total of 70 eligible participants will be randomized to the group with curcuminoids capsules and acupressure (C+A; group 1) or the group with placebo and sham acupressure (P+S; group 2) via lottery randomization. Thereafter subjects will be randomly allocated to C+A and P+S group. The schematic CONSORT (Consolidated Standards of Reporting Trials) flow diagram for the study protocol is presented in Figure 1. Schematic CONSORT (Consolidated Standards of Reporting Trials) flowchart for the study.

[figure not shown]

Figure 1. Schematic CONSORT (Consolidated Standards of Reporting Trials) flowchart for the study

Determination of baseline characteristics for every participant will be done by the therapist through a standardized assessment form. During the baseline measurement, the following characteristics will be recorded: sex, age, body mass, pain characteristic, history of disease and medication use. The participant's participation schedule will be determined according to the SPIRIT (Standard Protocol Items: Recommendations for Interventional Trials) statement Figure 2. The primary and secondary outcome measures will be recorded before providing the intervention.

[figure not shown]
TIMEPOINT**	STUDY PERIOD								
	Enrolment	Allocation	Post-allocation			Close-out			
		0	1 st week	2 nd week	3 rd week	1 st day	1 st week	2 nd week	Post 3 rd week
ENROLMENT:									
Eligibility screen	X								
Informed consent	X								
[Radiography and MMSE Test]	X								
Allocation		X							
INTERVENTIONS:									
[C+A Therapy]			X	X	X				
[P+S Therapy]			X	X	X				
ASSESSMENTS:									
[Demographic Details]	X								
[Inflammatory Marker]						X			X
[Endorphine]						X			X
[Quality of Life]						X	X	X	X

Figure 2. SPIRIT (Standard Protocol Items: Recommendations for Interventional Trials) recommended schedule for participation.

6 Intervention

After the standardized assessments and baseline measurements, the intervention will be conducted. Participants will be randomly assigned to the CA group or the PS group. For Acupressure Therapy and Sham Acupressure, each participant will be exposed to 3 therapy sessions per week of 20 minutes for 3 consecutive weeks. Participants will not be allowed to take any medication routinely during this time except for antihypertensive agents, thyroid medications, and antidiabetic drugs. To help participants adhere to the interventions, reminder messages will be sent before each session visit. For Curcuminoid capsules and placebo, Each participant will be exposed to taking capsules three times a day for 21 days.

Acupressure to perform CA, the patient is put in the supine position with legs straight. Prepare tools and materials such as a seat (or bed), warm water, olive oil, wet & dry tissue, towels. The therapist washes his hands, the client sits in a comfortable position. Teach patients breathing relaxation techniques to use during therapy. Give patients the opportunity to pray according to their respective beliefs. Make sure the client is relaxed and comfortable. Help remove the client's clothing or accessories that may hinder the acupressure action being performed, if necessary. Perform a client pain assessment. Wipe the client on the parts to be massaged with warm water that has been treated with a disinfectant solution using a small towel. Dry with a clean towel. Use cream or oil, do a warming massage with basic massage techniques, choose according to the client's condition (rubbing, squeezing, pressing) and stretching the patient's feet. Acupressure massage points are performed at ST34, ST36, Tai Xi Acupoint, GB34, SP 9, SP 8, EX-LE, EX-LE3, EX-LE4, EX-LE6, EX-LE7, EX-LE10

The patient is observed for a local twitch response. The patient is asked to report any abnormal sensations or discomfort during the course of intervention.

The sponsor will provide double-blind study medication for Curcuminoid and Placebo

Preparation of standardized curcuminoid turmeric extract preparations. Samples were made from extracted turmeric and then optimized. The capsule formulation is made from turmeric rhizome extract which contains 30 mg of curcuminoids per capsule. In the study, standardized curcuminoid turmeric extract was given in capsules at a concentration of 30 mg 3 times a day for 3 weeks.

7 Outcomes

All outcome measures will be assessed at baseline and after 3 weeks of intervention.

Primary Outcomes measures

1) Inflammatory Markers

Inflammation markers are carried out by measuring leukocyte numbers and the Neutrophil Lymphocyte Ratio. The examination is carried out using a complete blood test using a Hematology Analyzer, which is a laboratory tool used to measure and count the number of blood cells. The blood samples are mixed using a mixture of reagents to create a process called hemolyzing. This process will be divided into several purposes, to measure leukocytes, neutrophils, platelets and erythrocytes.

2) Secretion of the COX-2 hormone

The enzyme cyclooxygenase-2 (COX-2) is an important mediator in increasing the inflammatory response. In the blood plasma of patients with osteoarthritis, the COX-2 enzyme can be detected. The COX-2 hormone examination was carried out using the Enzyme Linked Immunosorbent Assay (ELISA) method on blood plasma.

3) Secretion of endorphin hormones

Endorphins, in this case beta endorphin, are hormones released by the pituitary gland in response to stress or pain, which are also secreted in blood plasma. Endorphin hormone levels in the blood were measured before starting therapy and after 3 weeks of therapy.

Endorphin hormone examination is carried out using the Enzyme Linked Immunosorbent Assay (ELISA) method on blood plasma that has been incubated at room temperature for 10-20 minutes, then the tube will be centrifuged for 20 minutes at a speed of 2000-3000 rpm.

Secondary outcomes

The effectiveness of therapy is the ability of the therapy regimen given to suppress several other expected output indicators. Other output indicators were measured before starting therapy and after 3 weeks of therapy

1) Knee pain as measured by the VAS score

2) Joint stiffness and joint functional ability are assessed by the WOMAC score.

WOMAC is a questionnaire developed by Bellamy (Bellamy et al., 1988) and continues to be developed to measure the functional abilities of patients with knee osteoarthritis. The WOMAC instrument has been translated into Indonesian and has been tested for validity by Karsten (Karsten et al., 2019) with the results of the Cronbach's Alpha coefficient of 0.966, indicating that there is relatively high internal consistency and is highly correlated, meaning that the WOMAC questionnaire in Indonesian is correct, validated and can be used by the Indonesian people. This questionnaire can evaluate 3 subscales, namely (1) pain (5 items), (2) stiffness (2 items) and (3)

physical function (17 items) by scoring on a 5-point ordinal scale. The details of the scores are (1) pain: score 0 "no pain", score 1 "mild pain", score 2 "moderate pain" score 3 "severe pain" and score 4 "very severe pain"; (2) stiff: score 0 "not stiff", score 1 "mildly stiff", score 2 "medium stiff", score 3 "extremely stiff" and score 4 "stiff to the point of locking"; (3) physical function: score 0 "not difficult", score 1 "somewhat difficult", score 2 "quite difficult", score 3 "very difficult" and score 4 "very difficult". Range of subscale scores for pain (0-20), stiffness (0-8) and physical function (0-68). The total score is obtained by adding up the scores of the 3 subscales, with a maximum score of 96. A higher WOMAC score indicates pain, stiffness and worse physical function. The total WOMAC score can be categorized into 3 groups, namely low risk (score ≤ 60), moderate risk (score 60-80) and high risk (score ≥ 81).

3) The independence of the elderly as assessed by the Barthel Index

The Barthel Index questionnaire was first developed in 1965 by Mahoney. Inventory of this instrument is held by The Maryland State Medical Society. Then in 2020, Pontansi (Pontung & et al, 2020) translated it into Indonesian and carried out a validity test with the result that inter-rater reliability was satisfactory.

In terms of content validity, the Indonesian version of the Barthel Index is acceptable. The construct validity test revealed two main factors, namely functional performance and physiological function.

4) Quality of Life assessed with KOOS

KOOS is an instrument to assess patient opinions about the condition of the knee and problems related to the knee. KOOS has been translated into Indonesian and tested for validity by Phatama (Phatama & et al, 2021) with Cronbach α results of 0.84 to 0.97 for all subscales, indicating adequate internal consistency. Test-retest reliability was excellent, with intraclass correlation coefficients ranging from 0.91 to 0.99 for all subscales. No significant differences were found in KOOS subscale responses between the first administration of the questionnaire and the second administration within 21 days. The Indonesian version of the KOOS was declared valid and reliable and therefore is an objective instrument for evaluating knee ligament injuries and knee osteoarthritis in the Indonesian population. KOOS can be used as a measurement of quality of life because it includes measurements of 5 subscales, namely (1) Symptoms; (2) Rigidity; (3) Pain; (4) Daily Activities; (4) Sports and Recreation Activities and (5) Knee-related Quality of Life. in circumstances one week prior is the time period considered when answering the question. Answer options are standard (Likert scale) and each question is scored from 0 to 4. Scores are normalized (a score of 100 indicates no symptoms and 0 indicates extreme symptoms).

8 Statistical Issues

Sample size

Sample size is estimated by the following formula

$$N = \frac{2\sigma^2(Z_{1-\alpha/2} + Z_{1-\beta})^2}{(\mu_1 - \mu_2)^2}$$

where N is the sample size required in both groups, σ is the standard deviation of the primary outcome. This research has a confidence level (1 - α) of 95%, so the value obtained is $\alpha = 5\%$. Therefore, the research hypothesis is unidirectional, so the magnitude of $Z_{1-\alpha} = 1.96$. Power (1 - β) in the research was also set at 80%, so that the value of $\beta = 20\%$ then the amount of $Z_{1-\beta} = 0.842$. Previous research analyzed changes in leukocytes in subjects treated with curcuminoid therapy from turmeric extract 30 mg 3 times a day for 14 days, amounting to 30.00 ± 5.10 and meloxicam 1 x 15 mg per day, obtained the mean delta value of leukocytes in the control group was $164.1+50.91$ and the treatment group was $174.27+78.93$.

$$N = \frac{2\sigma^2(Z_{1-\alpha/2} + Z_{1-\beta})^2}{(\mu_1 - \mu_2)^2}$$

$$= \frac{2(14,01)^2(1,96+0,842)^2}{(174,27-164,1)^2}$$

$$N = \frac{392,5602 (2,802)^2}{(174,27-164,1)^2}$$

$$N = \frac{3082,07}{103,4289}$$

$$N = 29,79 - (30 \text{ orang})$$

This gives the total number required in the 2 groups. Considering a dropout rate of 20%, the sample size should be increased to 36 each group.

9 Protection of Human Subjects and Assessment of Safety

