2.1 Primary objective

To determine the effectiveness of combination two regimens (acupressure and curcuminoid) as measured by changes from baseline (BL) in Leukocytes, Neutrophil Leukocyte Ratio, Blood Sedimentation Rate, Pain, secretion of COX-2 and Endorphin hormones in blood to placebo after 3 weeks of treatment in elderly patients with Osteoarthritis

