3.1 Study design

Randomized controlled trial, we will conduct a 2-arm, double-blind (patient and investigational blinded) to assess efficacy, tolerability and safety combination of acupressure and curcuminoid versus placebo.

Pre-Screening:

Patients can be pre-screened for certain x-ray and laboratory parameters. Following a screening visit, eligible subjects will enter the wash-out. After the wash-out period, eligible subjects will be randomized and treated for 3 weeks. The total duration of the study is up to 5 weeks.

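### The trial is called double-blind, but the acupressure therapist must know the arm and nothing keeps that person away from the subjective secondary scales

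*Combined protocol and SAP*

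**What the plan says.** Section 3.1 gives the design as "Randomized controlled trial, we will conduct a 2-arm, double-blind (patient and investigational blinded) to assess efficacy". The Protocol summary also uses the double-blind label. Neither mentions the acupressure therapist.

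Section 5 assigns controls to "the group with placebo and sham acupressure (P+S; group 2) via lottery randomization". On who assesses participants, it says "Determination of baseline characteristics for every participant will be done by the therapist through a standardized assessment form", and then that "the following characteristics will be recorded: sex, age, body mass, pain characteristic, history of disease and medication use". The same paragraph has the primary and secondary outcomes recorded before the intervention, without saying by whom.

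Section 6 sets out the acupressure session as the therapist's procedure: "The therapist washes his hands, the client sits in a comfortable position". A few steps later it says "Perform a client pain assessment". It also says that the sponsor supplies the curcuminoid and placebo capsules in blinded form. It has no corresponding statement for the acupressure.

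Section 3.2 restricts the group codes to the primary researcher. Section 9.3 gives the analysis to the secondary researcher and does not say whether that person is blinded. Section 7 lists VAS knee pain, WOMAC, the Barthel Index and KOOS as secondary outcomes and names no one to administer them.

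**The concern.** Half of the experimental treatment is delivered by hand. A capsule can be made to look the same in both arms. A person asked to give real acupressure to one participant and sham to another has to know which is which. A double-blind label without qualification therefore claims more than the design can deliver.

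What is at stake is the set of outcomes that depend on what a participant says or an interviewer judges. If someone who knows the arm hands out, reads aloud or prompts these scales, expectation can be conveyed differently in the two arms. The shift would then be part of the between-group difference. The tests in Section 9.3 (independent t or Mann-Whitney, paired t or Wilcoxon) could neither detect it nor remove it. A report that repeated the label would also overstate the strength of the evidence on pain, function and quality of life.

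**Working it through.** The point concerns who does what and who knows the arm, so the check is mainly a comparison of passages.

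1. **Who is said to be blinded.** Section 3.1 names the patient and an *investigational* party, presumably the investigator. The therapist is not covered in either direction.

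2. **Who can be blinded.**
   - Participant: plausible, given placebo capsules and sham acupressure (Section 5).
   - Capsule supply: stated as blinded (Section 6).
   - Therapist: not possible as described. Section 6 lists the points for real acupressure, the sham is not described, and no device or procedure to mask the provider is mentioned.
   - Primary researcher: holds the group codes (Section 3.2), which fits poorly with a blinded investigator.
   - Secondary researcher and laboratory: no statement. Section 3.2 implies at most that the secondary researcher lacks the codes.

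3. **Who assesses participants.** The therapist is named for baseline characteristics (Section 5). The pain assessment in Section 6 is a step in the therapist's session. No other role is named for recording a trial assessment on participants, and no sentence excludes the therapist from the scales.

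4. **When baseline is taken.** Section 6 mentions random assignment after the baseline measurements, and Figure 2 places demographic details at enrolment, before allocation. On that order the therapist does not yet know the arm. However, Section 5 requires outcome baselines only before the intervention, and Figure 2 seems to put the day-1 marker, endorphin and quality-of-life assessments in a column after allocation. The Figure 2 header is broken in the available text, so its alignment is uncertain. The order is unclear for the outcome measures.

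5. **Amount of contact.** Section 6 gives 3 sessions per week × 3 weeks = 9 sessions, and 9 × 20 minutes = 180 minutes, all before the 3-week ratings.

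6. **Which outcomes are exposed.** Section 7's primary outcomes are leukocyte count, the neutrophil-lymphocyte ratio, COX-2 and endorphin, all from an analyser or ELISA. They are little exposed. All four secondary outcomes are exposed to some degree. Pain has an unclear rank: Section 2.1 puts it in the primary objective ("Blood Sedimentation Rate, Pain, secretion of COX-2 and Endorphin hormones in blood to placebo"), while Section 7 makes VAS secondary and the summary's data-analysis entry omits it from the primary efficacy variables.

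No magnitude can be calculated. The documents give no variability or expected effect for VAS, WOMAC, the Barthel Index or KOOS, and no figure for the effect of an unblinded assessor.

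**The case against.** The strongest reply is that the plan never says an unblinded person rates an outcome. Four inferences are tempting, and the documents do not support them.

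- **That baseline pain is recorded unblinded.** The Section 5 sentence covers descriptive characteristics that probably precede allocation. If they do, it causes no harm by itself.
- **That the session pain assessment is the VAS outcome.** In Section 6 it is a preparatory step, written only for the active arm. Section 7 takes outcomes at baseline and after 3 weeks, and nothing links the two.
- **That one therapist sees each participant for all nine sessions and then takes the 3-week ratings.** Sections 5 and 6 both refer to the therapist, but do not say it is one person, and the final rater is not named.
- **That the primary results are compromised.** The Section 7 primary outcomes are laboratory measures.

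It is also fair to say that KOOS and WOMAC are patient questionnaires, that participants are meant to be blinded, and that Section 4.3 uses the MMSE so that participants can follow the outcome measurement. Self-completion may already be the intended practice.

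These points reduce the claim from bias to risk of bias. They do not answer the two facts that remain. The label is unqualified although the hands-on half of the treatment cannot be blind to its provider, and the plan contains nothing that separates that provider from the subjective scales.

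**Conclusion.** The concern holds as a mismatch between the stated blinding and the design, together with an unguarded risk of bias in four subjective secondary outcomes. It should be corrected. It does not undermine the laboratory primary outcomes. The size of any bias is unknown.

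The conclusion rests on three assumptions. The provider can tell the sham from real acupressure, which follows from having to perform it. The codes in Section 3.2 reveal the arm, as their description by group suggests. The silence on who administers the scales is a real absence in the protocol text. If pain is treated as primary, in line with Section 2.1, the risk extends to a primary outcome and the correction matters more.

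**What to change.** 1. In Section 3.1 and the Protocol summary, describe the trial as participant-blinded, with the acupressure therapist and the holder of the group codes not blinded. Claim assessor, analyst or laboratory blinding only if the protocol also states that those people have no access to the codes. Otherwise one unsupported claim replaces another.
2. In Sections 5 and 6, state that all baseline measures, including the scales, are completed before allocation, and align Figure 2 with this.
3. In Section 7, have VAS, WOMAC and KOOS self-completed by the participant out of the therapist's presence.
4. Have the Barthel Index taken, and any reading help given, by an existing team member who neither treats participants nor has access to the codes. The secondary researcher could do this if kept blind and if the protocol says so.

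The cost is wording and a change in who handles the forms. No new post should be needed if an existing team member can take this on. The downside is that some elderly participants will need help with the forms, which takes that person's time. The change has to be made before ratings are collected, because a prompted rating cannot be repaired in the analysis.

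### The sample size enters 14.01 as the standard deviation when the quoted SDs are 50.91 and 78.93, so the stated 80% power for the planned leukocyte difference is really about 9%

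*Combined protocol and SAP*

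**What the plan says.** Section 8 (Sample size) uses the standard formula for comparing two means and states that "σ is the standard deviation of the primary outcome". It takes leukocyte change from previous research as the basis: "obtained the mean delta value of leukocytes in the control group was $164.1+50.91$ and the treatment group was $174.27+78.93". The numerator of the worked formula is then "2(14,01)^2(1,96+0,842)^2", so sigma is 14.01, and the denominator is the square of 174.27 − 164.1. The result is 29.79, rounded to 30, then raised to 36 per group for 20% dropout. On power the section says "Power (1 - β) in the research was also set at 80" per cent. On direction it says "Therefore, the research hypothesis is unidirectional", yet the critical value is 1.96. Section 5 randomises 70 participants to two groups. The section does not say where 14.01 comes from, and this is the only sample size calculation in the document.

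**The concern.** The difference of 10.17 and the two spreads come from the same sentence, but only the difference is carried into the formula. The sigma of 14.01 is less than a third of the smaller spread, and required sample size grows with the square of sigma. If sigma is wrong, so is the 80% power that justifies randomising about 70 people aged 65 or over. Section 9.3 plans significance tests at 0.05 and no confidence interval for the difference between groups. A trial with very low power would then probably give a non-significant leukocyte result that readers take as evidence of no effect.

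**Working it through.** **Inputs (all from Section 8 unless noted).** Control: mean 164.1, SD 50.91. Treatment: mean 174.27, SD 78.93. Difference: 174.27 − 164.1 = 10.17. Multipliers: 1.96 and 0.842, sum 2.802. The plus sign is read as plus-or-minus, as in the 30.00 ± 5.10 printed in the same sentence. N is taken as per group, which is what the formula gives and what 36 each implies.

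**Reproducing the plan.** N = 2 × 14.01² × 2.802² / 10.17² = 3082.07 / 103.43 = 29.80, which the plan prints as 29.79 and rounds to 30. A one-sided 5% critical value would give 24, so the plan's figure rests on 1.96.

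**Where 14.01 may come from.** (78.93 − 50.91)/2 = 28.02/2 = 14.01, an exact match. Half the gap between two SDs does not measure the spread of the outcome.

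**What the quoted figures imply.** Any pooled or weighted SD must lie between 50.91 and 78.93. With equal group sizes in the earlier study it is √((50.91² + 78.93²)/2) = 66.41. The planned difference is therefore 10.17/66.41 = 0.15 SD, where the plan's calculation implies 10.17/14.01 = 0.73 SD.

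**Power for a difference of 10.17, 30 per group, two-sided 0.05 (noncentral t).**

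| SD used | Power | N per group for 80% |
|---|---|---|
| 50.91 | 11.9% | 394 |
| 66.41 (pooled) | 9.0% | 670 |
| 78.93 | 7.8% | 946 |

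The last column uses the plan's own formula; for the pooled SD it is 2 × 66.41² × 2.802² / 10.17² ≈ 670. The normal approximation gives 8.6% power at the pooled SD, or 9.1% with both tails counted.

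**Other group sizes, pooled SD.** If 70 are split equally (no ratio is stated, so this is an assumption) and 20% drop out, 35 × 0.8 = 28 per group are evaluable and power is 8.7%. At 36 per group with no loss it is 9.8%.

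**One-sided reading.** With a one-sided 0.05 test, power at 30 per group is 14.5%, and 528 per group would be needed.

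**What the size can detect.** With SD 66.41 and two-sided 0.05, 80% power is reached at a difference of 48.9 (0.74 SD) with 30 per group and 50.6 (0.76 SD) with 28. Both are nearly five times 10.17. The expected 95% confidence half-width at 28 per group is 2.005 × 66.41 × √(2/28) ≈ 36.

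**The case against.** The strongest reply is that 9% is not the power of this trial in general. It applies to a true difference of 10.17 in leukocytes. The sentence supplying that difference names meloxicam, whereas this trial compares with placebo plus sham acupressure, and the documents give no expected difference against that control. Section 8 also states neither unit nor specimen for the leukocyte change. The curcuminoid study described in Section 1.1 measured synovial fluid, while Section 7 measures blood, so 66.41 may not be on the scale this trial will use. In addition, the origin of 14.01 is inferred, leukocytes are only one of several primary outcomes, and the one-sided wording leaves the test open to interpretation.

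Most of this limits the scope of the point; none of it rescues the calculation. The plan's 80% is itself a claim about 10.17 in leukocytes, so 9% against 80% compares like with like. If the earlier data are on the wrong scale, the difference of 10.17 falls with them. Whatever produced 14.01, it is incompatible with the SDs printed beside it. A one-sided test raises power only to 14.5%. What stands is that the 9% must be stated as conditional on 10.17 and on leukocytes, that it says nothing about COX-2, endorphin or the neutrophil ratio, and that figures in leukocyte units need their scale confirmed. The detectable difference in SD units does not depend on that scale.

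**Conclusion.** The concern holds. The sigma in Section 8 is not a standard deviation that the quoted data can support, and the 80% power claim for a leukocyte difference of 10.17 is wrong: on the plan's own inputs power is about 9%. The conclusion assumes that the plus signs mean plus-or-minus and, for the central figure, equal group sizes in the earlier study. If 50.91 and 78.93 were standard errors, the SDs would be larger and power lower still. Unequal group sizes would move power only within 7.8% to 11.9% at 30 per group. The meloxicam comparator and the clash between a one-directional hypothesis and the two-sided 1.96 are lesser faults in the same calculation; the main result does not depend on them.

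**What to change.** In Section 8:

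- Replace 14.01 with the pooled SD of about 66.4, showing how it is obtained and giving the unit and specimen of the earlier measurements.
- Delete the claim of 80% power for 10.17. State instead that the fixed size gives about 9% power for that difference, and 80% power only for about 49 to 51 units (0.74 to 0.76 SD) with 30 to 28 evaluable per group.
- Say that 10.17 comes from a study that involved meloxicam, not placebo plus sham.
- State that the test is two-sided at 0.05, consistent with 1.96, and remove the one-directional wording.
- Commit to reporting the leukocyte difference with its 95% confidence interval (expected half-width about 36 units at 28 per group), and repeat this in Section 9.3.

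The target of about 70 patients can stay, justified by the detectable difference and the precision. The cost is wording only. The stated power becomes much less favourable, and a non-significant leukocyte result could no longer be presented as showing no effect.
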